7 STUDY DRUG DISCONTINUATION AND PARTICIPANT WITHDRAWAL

7.1 Study Drug Discontinuation

Subjects may voluntarily discontinue study drug at any time. The Investigator and/or Sponsor may also discontinue a subject's study drug at any time. Study drug will be discontinued in subjects who experience individual treatment-stopping criteria described in this section. The Sponsor and Investigator will make efforts (when possible) to continue to collect data (according to the Schedule of Treatment Period and Follow-up Activities) on subjects who discontinue study drug.

When feasible, Investigators should discuss any safety concerns with the Medical Monitor as soon as possible to determine whether a subject should continue or discontinue study drug.

If study drug is discontinued, the Investigator will report the discontinuation to the Medical Monitor, document the date and reason for study drug discontinuation on the appropriate electronic case report form (eCRF), schedule an early termination visit for the subject (see the Schedule of Treatment Period and Follow-up Activities in [Section 1.3.3](#)), provide or arrange for appropriate follow-up, and document the course of the subject's condition.

7.1.1 Liver Chemistry Stopping Criteria

Liver chemistry stopping criteria defined in [Table 3](#) are designed to ensure subject safety and to evaluate liver event etiology. The Investigator should notify the Sponsor within 24 hours of awareness if any of the criteria defined in [Table 3](#) are met. Further suggested actions, follow-up assessments, and monitoring assessments are provided in [Section 13.2](#). A significant change in liver chemistry that requires increased monitoring but does not necessarily satisfy stopping criteria may still be considered an adverse event of special interest (AESI) (see [Section 8.3.8](#)).

Table 3. Stopping Criteria and Increased Monitoring for Liver Chemistry Elevations

Criteria		Action
ALT \geq 5x ULN		Discontinue study drug and notify Sponsor
ALT \geq 3x ULN	AND total bilirubin \geq 2x ULN ($>35\%$ direct bilirubin) ¹	Discontinue study drug and notify Sponsor Possible Hy's Law case— report as SAE
	AND INR >1.5	Discontinue study drug and notify Sponsor. Possible Hy's Law case— report as SAE
	AND subject has symptoms (new or worsening) believed to be related to liver injury or hypersensitivity ²	Discontinue study drug and notify Sponsor
	AND total bile acids $>3x$ ULN	Withhold study drug and notify Sponsor. Repeat liver chemistry tests after 1 week and discuss with Medical Monitor whether to discontinue study drug.
	ALT \geq 3x ULN only	Monitor weekly for 4 weeks while continuing study drug and notify Sponsor (see Section 13.2.2)
	AND cannot be monitored weekly for 4 weeks	Discontinue study drug and notify Sponsor
persists for \geq 4 weeks		Discontinue study drug and notify Sponsor

Abbreviations: ALT, alanine aminotransferase; INR, international normalized ratio; SAE, serious adverse event; ULN, upper limit of normal.

¹If serum bilirubin fractionation is not immediately available, discontinue study drug if ALT \geq 3x ULN and bilirubin \geq 2x ULN and record the presence/absence of detectable urinary bilirubin on dipstick, which is indicative of direct bilirubin elevations suggesting liver injury.

²Symptoms related to liver injury include fatigue, nausea, vomiting, right upper quadrant pain or tenderness, and jaundice. Symptoms related to hypersensitivity include fever, rash, and eosinophilia.

7.1.2 QT Stopping Criteria

Study drug will be discontinued for a subject if either of the following criteria is met:

- QTcF >500 msec OR uncorrected QT >600 msec
- Change from screening or baseline in QTcF of >60 msec

One repeat ECG should be performed to confirm the accuracy and persistence of an initial result that fulfills the QT stopping criteria.

7.1.3 Suicidality Stopping Criteria

Tildacerfont is considered to be a central nervous system (CNS)–active drug. Some CNS-active drugs may be associated with an increased risk of suicidal ideation in certain populations. Although tildacerfont has not been shown to be associated with an increased risk of suicidal

thinking or behavior in past clinical studies, subjects will be monitored for such events during this study using the C-SSRS (see [Section 8.2.6.1](#)).

Individuals who answer “yes” to Question 3, 4, or 5 in the suicidal ideation section of the C-SSRS at screening or baseline are not eligible for this study. Any subject who exhibits any Suicidal Behavior or Suicidal Ideation (eg, answers “yes” to Question 3, 4, or 5 in the suicidal ideation section of the C-SSRS) will have study drug immediately discontinued and should be evaluated by a psychiatrist. This safety finding will be considered an AESI if it is not an SAE (e.g., requiring hospitalization) (see [Section 8.3.8](#)).

7.1.4 Depression or Anxiety Stopping Criteria

Individuals who score >12 on either the depression or anxiety subscale of the HADS (see [Section 8.2.6.2](#)) at screening or baseline are not eligible for this study. Any subject who develops severe depression or anxiety (Common Terminology Criteria for Adverse Events [CTCAE] Grade 3 or higher), as assessed by the Investigator, will require study drug discontinuation and appropriate follow-up. This will be considered an AESI if it is not an SAE (eg, requiring hospitalization) (see [Section 8.3.8](#)).

7.1.5 Adrenal Insufficiency Stopping Criteria

Symptoms of adrenal insufficiency include weakness, tiredness, anorexia, nausea, vomiting, abdominal pain, orthostasis and muscle and joint aches. Weight loss and hypotension (ie, systolic blood pressure <90 mmHg) are also associated with adrenal insufficiency.

Hyponatremia, hyperkalemia, hypercalcemia, azotemia, anemia and eosinophilia may accompany adrenal insufficiency. It is important to note that many of these signs, symptoms and laboratory findings are nonspecific and commonly occur in persons without adrenal insufficiency. The Investigator should use their clinical judgment when determining whether the signs, symptoms or laboratory findings are isolated adverse events or are possibly due to adrenal insufficiency.

The Investigator is strongly encouraged to contact the Medical Monitor to review the presentation and discuss the plan for a subject with any potential adverse events of adrenal insufficiency.

If the Investigator deems the sign(s), symptom(s) and/or laboratory finding(s) to be due to adrenal insufficiency, the adverse event should be recorded as adrenal insufficiency. The sign(s), symptom(s) and laboratory findings resulting in the diagnosis of adrenal insufficiency will be collected on separate Adrenal Insufficiency Adverse Event CRF and should not be recorded on the Adverse Event CRF.

If a subject develops an adrenal insufficiency AE meeting the SAE definition ([Section 8.3.2](#)) or the definition of an adrenal crisis ([Section 4.1.4.4, Table 2](#)), the Investigator should discuss with Medical Monitor (in cases where a clear explanation for the occurrence of adrenal insufficiency or adrenal crisis is identified, discontinuation of the study medication is not necessary). If there is no clear explanation for serious event of adrenal insufficiency, then PI may discuss further steps with medical monitors.

If the subject develops adrenal insufficiency due to undertreatment (as opposed to an acute stressor), the subject's daily GC dose should be increased by 5 mg HCe and should not be reduced again to the GC dose level associated with adrenal insufficiency (per Investigator judgment and discussion with the Medical Monitor). Study drug should not be discontinued but may be interrupted while GC dose adjustment is made.

In the absence of any clear explanation for the subject's acute adrenal insufficiency, the Investigator should discontinue study drug. This will be considered an AESI (see [Section 8.3.8](#)).

Adverse events or other conditions that lead to GC stress dosing should not be reported as AEs of adrenal insufficiency since the stress dosing is done to prevent, not treat, adrenal insufficiency.

7.1.6 Reproductive Hormone Stopping Criteria

If a subject experiences significant changes from baseline in reproductive hormone(s), the Investigator should determine whether such changes represent clinically significant reproductive abnormalities, potential risks to the subject, whether to discontinue study drug, and appropriate safety follow-up. These changes include but are not limited to significant changes in LH, FSH, or SHBG; significant changes in inhibin B or testicular dysfunction in men; and significant changes in estradiol, prolactin, progesterone, or menstrual cyclicity in women.

Investigators should keep in mind that subjects with CAH can be expected to have abnormal reproductive hormone levels because deficient 21-hydroxylase enzyme activity leads 1) to elevated levels of cortisol precursors that are shunted into reproductive hormone biosynthetic pathways and 2) to low levels of the cortisol that normally provides negative feedback on the HPA axis. Standard-of-care therapy with GC and mineralocorticoid replacement does not necessarily fully normalize adrenal steroid production pathways and signaling systems, including ACTH and CRF levels. Thus, subjects with CAH can be expected to have abnormal plasma concentrations of various androgens and progestogens at baseline. Therapy with an effective CRF receptor antagonist may in fact shift the balance between various intermediates in the steroid biosynthetic pathway. Investigators should inform the Medical Monitor before discontinuing study drug.

7.1.7 Clinically Significant Adverse Event Stopping Criteria

The Investigator should consider study drug discontinuation and appropriate safety follow-up for a subject who experiences a clinically significant AE. When feasible, the Investigator should contact the Medical Monitor to discuss the subject's clinical condition before discontinuing study drug. Clinically significant AEs include but are not limited to study drug-related SAEs ([Section 8.3.2](#)) and study drug-related AESIs ([Section 8.3.8](#)).

7.2 Participant Withdrawal from the Study

Subjects are free to withdraw from the study at any time upon request. If the subject withdraws consent for disclosure of future information, the Sponsor may retain and continue to use any data collected before the withdrawal of consent. The subject may request destruction

of any samples taken and not tested, and the Investigator must document this in the site study records.

Subjects will be withdrawn from the study by the Investigator and/or Sponsor for either of the following:

- Pregnancy
- If any clinical AE, laboratory abnormality, or other medical condition or situation occurs such that continued participation in the study would not be in the best interest of the subject

A subject may also be withdrawn from the study by the Investigator and/or Sponsor at any time for other safety, behavioral, compliance, or administrative reasons such as the following:

- Significant protocol deviation or noncompliance with study procedures/restrictions
- If the subject no longer meets eligibility criteria
- Study termination by the Sponsor

Subject withdrawal is expected to be uncommon. If possible, an early termination visit (as shown in the Schedule of Treatment Period and Follow-up Activities in [Section 1.3.3](#)) should be conducted before subject withdrawal. The Investigator must document the date and primary reason for the withdrawal on the appropriate eCRF. Subjects who withdraw prematurely may be replaced at the discretion of the Sponsor to ensure adequate numbers of evaluable subjects.

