5.1 Eligibility Criteria

5.1.1 Inclusion Criteria

A subject must meet all of the following criteria to be eligible for this study:

1. Male and female subjects ≥ 18 years old at screening
2. Has a known childhood diagnosis of classic CAH due to 21-hydroxylase deficiency based on genetic mutation in *CYP21A2* and/or documented (at any time) elevated 17-OHP and

currently treated with HC, HC acetate, prednisone, prednisolone, methylprednisolone, dexamethasone (or a combination of the aforementioned GCs)

3. Has LLD \leq A4 \leq 2.5x ULN at screening measured before an AM GC dose
4. Has been on a stable, supraphysiologic dose of GC replacement (defined as \geq 30 mg/day and \leq 60 mg/day in HCe) for \geq 1 month before screening
5. For subjects with the salt-wasting form of CAH, subject has been on a stable dose of mineralocorticoid replacement for \geq 1 month before screening
6. Agrees to follow contraception guidelines ([Section 5.2.5](#)). Male subjects must also agree to refrain from donating sperm throughout the Treatment Period and for 90 days after the last dose of study drug
7. Is able to understand all study procedures and risks involved and provides written informed consent indicating willingness to comply with all aspects of the protocol

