 - d. Total bile acids >5x ULN
8. Routinely works overnight shifts
9. Subjects with travel plans/work schedules that result in significant and frequent changes in time zones (>2 hours) will require Medical Monitor approval for enrollment
10. Females who are pregnant or nursing
11. Use of any other investigational drug from 30 days or 5 half-lives (whichever is longer) before screening to the end of the study
12. Use of the following drugs from 30 days or 5 half-lives (whichever is longer) before the start of the Treatment Period to the end of the study:
 - a. Rosiglitazone, aromatase inhibitors, testosterone, growth hormones, or any other medication or supplement that could impact subject safety or confound interpretation of study results
 - b. The drugs listed in **Section 13.1**, which are:
 - i. Moderate to strong inhibitors and/or inducers of CYP3A4
 - ii. Sensitive substrates or narrow-therapeutic-range substrates of CYP3A4 (except hormonal contraception containing ≤ 35 μ g ethinyl estradiol)
 - iii. Sensitive substrates or narrow-therapeutic-range substrates of BCRP (except those that can be administered QD in the morning, separated by approximately 10 hours from evening administration of study drug)
13. Donation or receipt of blood from 90 days before Screening to the end of the study; donation or receipt of platelets, white blood cells, or plasma from 30 days before Screening to the end of the study

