12.3.1 Definition of Primary Efficacy Endpoint Estimand

The primary “treatment policy” estimand is the absolute change from baseline in GC dose in HCe at Week 24 post randomization. In the original study protocol, the primary endpoint was defined in a binary fashion as the proportion of subjects with at least a 5 mg/day HCe reduction from baseline in GC dose and $A4 \leq ULN$ at Week 24. Consistent with the emerging analysis of competitor trial data, and also realizing the loss of information and power associated the reduction of continuous data to a simple binary form, the primary endpoint definition was changed from binary to a continuous change from baseline and, hence, the associated use of MMRM analysis below. Nevertheless, binary evaluation of the primary endpoint is still retained in the SAP in the form of supportive secondary analyses.

Population: The analysis population is the ITT analysis set, including all classic CAH subjects who were randomized into the study

Variable: The analysis variable is the absolute change from baseline to Week 24 in GC dose in HCe.

Intercurrent events: For the Primary Efficacy Endpoint analysis, intercurrent events such as changes in GC type or lack of treatment compliance or GC compliance, treatment interruption or discontinuation, use of prohibited medications will be ignored.

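### Protocol 7.2 allows withdrawal from the study for lost eligibility or noncompliance, events the primary estimand ignores, so Week 24 data that the analysis needs may be lost

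*Protocol*

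**What the plan says.** Protocol 7.2 has a mandatory list (pregnancy, and medical situations in which staying is not in the subject's interest) and a discretionary one. The discretionary list opens with "A subject may also be withdrawn from the study by the Investigator and/or Sponsor at any time". Its examples include "Significant protocol deviation or noncompliance with study procedures/restrictions" and "If the subject no longer meets eligibility criteria". An early termination visit is held beforehand where possible, and "Subjects who withdraw prematurely may be replaced at the discretion of the Sponsor to ensure adequate numbers of evaluable subjects".

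Several entry criteria can be failed after randomisation. Exclusion 12 (the interacting drugs of Section 13.1 and others) applies from a washout "before the start of the Treatment Period to the end of the study". Exclusions 11 (other investigational drugs) and 13 (giving or receiving blood or blood components) have the same end point. Exclusion 4 (signs or symptoms of adrenal insufficiency) carries no date.

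SAP 12.3.1 calls the primary estimand treatment policy and defines it in all randomised subjects. Changes of glucocorticoid (GC) type, noncompliance, treatment interruption or discontinuation, and "use of prohibited medications will be ignored".

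For subjects who stop study drug, Protocol 7.1 says: "The Sponsor and Investigator will make efforts (when possible) to continue to collect data". Section 7.2 has no matching sentence for subjects withdrawn from the study.

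**The concern.** A treatment-policy estimand can disregard an event only if the outcome is still observed after it. Section 7.2 permits follow-up to end because of events on the SAP's list of things to disregard. A subject who takes a prohibited antibiotic or antifungal at Week 10, or who adheres poorly, could leave with no Week 24 GC dose although nothing prevented its collection.

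The loss may be informative. Poor adherence to study drug or GC, intercurrent illness and symptoms suggesting adrenal insufficiency can all plausibly be related to the GC dose a subject would have reached. The retrieved-dropout imputation, named as the missing-data approach in Protocol 9.4.1 and as an additional analysis in SAP 12.3.3.1(d), borrows from subjects who stop drug yet stay in follow-up. A discretionary withdrawal can add a missing value and remove a possible donor at once.

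**Working it through.** **1. Which criteria can be lost after randomisation**

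| Criterion | Time frame | Can be failed later? |
|---|---|---|
| Inclusion 3 (A4 range) | at screening | no |
| Inclusion 4 (GC 30 to 60 mg/day) | at least 1 month before screening | no |
| Exclusion 4 (adrenal insufficiency) | none given | yes, if applied after entry |
| Exclusions 11, 12, 13 | until study end | yes |

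The Section 13.1 list includes ciprofloxacin, fluconazole, loperamide and oseltamivir. Protocol 6.5 itself anticipates new antibiotics and cold remedies during the study. The trigger is realistic.

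**2. The same events under each rule**

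| Event | Protocol 7.2 | SAP 12.3.1 |
|---|---|---|
| Prohibited drug | may be withdrawn (lost eligibility) | disregarded; Week 24 value needed |
| Noncompliance | may be withdrawn | disregarded; Week 24 value needed |
| Blood donation | may be withdrawn (lost eligibility) | not listed; subject remains in the ITT set |

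**3. What data remain after withdrawal.** The early termination visit in Protocol 1.3.4 includes hormones and background GC dosing. SAP Table 12 sets the Week 24 window at Days 149 to 197, so a termination visit before Day 149 supplies no Week 24 value. A replacement subject does not fill the gap, because the withdrawn subject stays in the ITT set.

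**4. Adrenal insufficiency.** Where undertreatment is the cause, Protocol 7.1.5 says study drug is not to be discontinued, though it may be interrupted. Exclusion 4 read with 7.2 would permit withdrawal of the same subject from the study. These passages do not agree.

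**5. Size**

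Inputs from SAP 6: difference 5 mg/day, SD 6.9 mg/day, two-sided alpha 0.05, 40 per arm for 90% power. Planned size is 45 per arm (Protocol 9.2).

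Power = Φ(difference / (SD × √(2/n)) − 1.96).

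- Plan's own figure, n = 40: 5 / (6.9 × √(2/40)) = 3.241; Φ(1.281) = 0.900. It reproduces (0.893 with the t distribution).
- n = 45: 5 / (6.9 × √(2/45)) = 3.437; Φ(1.477) = 0.930.

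One subject is 1/45 = 2.2% of an arm. The documents give no withdrawal rate, so the shares below are assumptions:

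| Share per arm without a Week 24 value | n | Power |
|---|---|---|
| 0% | 45 | 0.930 |
| 5% | 42.75 | 0.918 |
| 10% | 40.5 | 0.903 |
| 20% | 36 | 0.867 |

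Power is not the main issue. If a share w of one arm is withdrawn and its true mean change differs by d from that of the retained subjects, the observed arm mean is off by w × d before any imputation:

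| w | d = 2.5 | d = 5 | d = 10 mg/day |
|---|---|---|---|
| 5% | 0.12 | 0.25 | 0.5 |
| 10% | 0.25 | 0.5 | 1.0 |
| 20% | 0.5 | 1.0 | 2.0 |

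The yardstick is the 5 mg/day design difference. Both w and d are assumed.

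**The case against.** The case for leaving the text alone has substance. The rule is permissive, and 7.2 expects withdrawals to be rare. Nothing requires withdrawal after a prohibited drug. Protocol 6.5 and 6.5.1 send such cases to the site and the Medical Monitor. SAP 11.3.1 tabulates prohibited medication, SAP 10.2 classes it as a major deviation, and SAP 7.3 handles low adherence through the Per-Protocol set. All of this presumes that the subjects stay. The mixed model uses every visit from Week 3, and MAR, placebo-based, retrieved-dropout and (if the endpoint is met) tipping-point analyses are planned. Strictly, 7.1 and 7.2 do not contradict each other, since one concerns leaving study drug and the other leaving the study.

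These points limit the size of the problem without removing it. Sensitivity analyses show how much missing values could matter but cannot supply values that could have been collected. That other sections presume retention is a reason to make 7.2 say so.

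A reader might go further and infer that 7.2 reaches the trial's own successes and failures: a subject reduced below 30 mg/day, or one whose A4 rises above 2.5 times ULN. The text does not support this. Inclusion 4 begins "Has been on a stable, supraphysiologic dose of GC replacement" but then dates that requirement to the period before screening, and inclusion 3 is dated at screening. A later dose or A4 value cannot undo either. Protocol 4.1.4.3 also directs GC reductions and increases as the normal course of the trial.

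**Conclusion.** The point holds as a mismatch between a discretionary withdrawal rule and the primary estimand. Section 7.2 allows follow-up to end for prohibited-drug users, noncompliers and others who breach an exclusion that lasts until study end. SAP 12.3.1 disregards noncompliance and prohibited medication and so needs the Week 24 dose of these subjects. The protocol's commitment to keep collecting data does not extend to anyone withdrawn from the study.

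The rule may remove needed data. The documents do not show that it will, or how often. Loss of power is modest under the assumed rates (0.903 with 10% missing per arm). The greater risk is avoidable and possibly informative missing data, with an illustrative shift of 0.25 to 1.0 mg/day at 10% in one arm. It would go too far to say that the primary result would rest on imputation. The change is worth making because it is cheap and specific.

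**What to change.** Reconcile Protocol 7.2 with Protocol 7.1 and SAP 12.3.1:

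- Remove loss of eligibility, and protocol deviation or noncompliance, as stand-alone grounds for withdrawal from the study after randomisation. Leave the mandatory grounds as they are.
- State that such subjects continue scheduled visits, with GC dose and A4 collected, through Week 24, on or off study drug, unless they withdraw consent or safety requires withdrawal.
- Leave study-drug decisions to the existing protocol provisions; no new rule is needed for this purpose.
- Reconcile exclusion 4, Section 7.1.5 and Section 7.2 on adrenal insufficiency, so that it is clear whether exclusion 4 applies after entry.

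The cost is a protocol wording change. The visits are already in the schedule, so the practical burden is a few more visits for subjects who would otherwise have left. Deviations can still be handled through the Per-Protocol set.
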